#### **7.2.2.8. Non-Relapse Mortality**

Cumulative incidence of non-relapse mortality at Days 180 and 360 post-first study treatment with ALXN1007 will be analyzed using similar methods as described above for acute GVHD flares with relapse related death as competing risk.

#### **7.2.3. Pharmacokinetic and Pharmacodynamic Analyses**

No analyses on PK and PD parameters will be produced for the abbreviated CSR.

#### **7.2.4. Exploratory Biomarker Analyses**

No analyses on exploratory biomarkers will be produced for the abbreviated CSR.

### **7.3. Safety Analyses**

All safety analyses will be conducted on the Safety Set. No formal hypothesis testing is planned. Baseline is defined as the last available assessment prior to the first dose of ALXN1007.

#### **7.3.1. Study Duration, Treatment Compliance, and Exposure**

For each dosing visit, number (%) of patients with study treatment administered, total dose (mg) will be summarized by descriptive statistics. The study dose (mg) will be calculated as 5×mL administered when incomplete dose is administered, note that per pharmacy manual, the final conc. is 5mg/ml.

#### **7.3.2. Adverse Events (AEs)**

Treatment-Emergent Adverse Events (TEAEs) will be tabulated and presented separately. AEs will be coded by primary system organ class and preferred term using the Medical Dictionary for Regulatory Activities (MedDRA).

##### **7.3.2.1. Overall Summary of Adverse Events**

An overall summary of TEAEs and non-fatal serious TEAEs and non-serious TEAEs will be presented. The number of events (n) and number (%) of patients with events will be shown for the following event subcategories:

**Table 4. Subcategories For Treatment-Emergent Adverse Events (TEAEs)**

Relationship: Related AEs (possibly, probably, or definitely related), Not Related AEs (not related or unlikely)
Severity: Grade 1,2,3,4,5
Leading to withdrawal

**7.3.2.2. AEs and SAEs by System Organ Class (SOC) and Preferred Term (PT)**

The number of TEAEs and the number (%) of patients with events will be presented by SOC and PT. Patients are counted once in each SOC and PT. The ordering of SOC and PT is to be done by the most prevalent SOC in the overall ALXN1007 group reporting any AEs in that SOC, then by most prevalent PT reporting any AEs in that SOC. For SOC/PT with same number of patients (e.g., to break ties) they should be further sorted by number of events (when applicable) and then alphabetically. Similar tabulations will be done for SAEs and non-SAEs separately. Additionally tabulations by PT only will be produced for TEAEs and SAEs where PTs will be sorted by the most prevalent AEs in that PT in the overall ALXN1007 group.

**7.3.2.3. AEs and SAEs by SOC, PT, and Relationship**

Summaries of TEAEs and TESAEs by grouped relationship (related/not related) to treatment will be provided by SOC and PT.

**7.3.2.4. AEs and SAEs by SOC, PT, and Toxicity Grade**

Summaries of TEAEs and TESAEs by SOC, PT and CTC toxicity grades will be provided.

**7.3.2.5. Deaths, Other SAEs and Other Significant Adverse Events**

Summaries of TEAEs leading to death will be provided by SOC and PT. Summaries of TEAEs leading to study treatment discontinuation will be provided by SOC and PT.

**7.3.3. Other Safety**

Baseline for safety assessment (i.e. laboratory values, vital signs) will be defined as last non-missing value prior to 1st ALXN-1007 infusion.

**7.3.3.1. Analyses for Laboratory Tests**

Descriptive statistics by visit will be presented for each laboratory parameter (as mentioned in Section 5.2.3). Changes from Baseline as well as shift tables for laboratory parameters will be presented. All laboratory values will be classified as normal, below normal (low), or above normal (high) based on normal ranges supplied by the central laboratory. Frequencies of abnormal values will be presented in tabular form. Similar tabulations will be provided based on CTC toxicity grades. For purposes of analyses, laboratory results based upon standardized units will be used.

**7.3.3.2. Vital Signs**

Changes from baseline in vital signs will be summarized by visit.

### 7.3.3.3. Physical Examination

A by-patient listing will be produced for physical examination; no tabular summaries will be generated.

### 7.3.3.4. Electrocardiograms (ECG)

A by-patient listing will be produced for ECG; no tabular summaries will be generated.

### 7.3.3.5. Immunogenicity

A by-patient listing will be produced for anti-bodies to ALXN1007; no tabular summaries will be generated.

## 7.4. Interim Analyses

The following interim data analyses will be performed during the study.

- This study has a stopping guideline for excessive mortality (refer protocol Section 7.5.2). A stopping rule for Day 56 mortality will be applied after every 6 patients are accrued. The study will be stopped at interim evaluation (t) if the number of deaths is  $\geq X_t$ , e.g., if 4 or more deaths in the first 6 patients or 6 or more deaths in the first 12 patients, etc., as detailed in Table 4 below. A 20% mortality rate, which is anticipated based on historical data, will have a 2.6% chance of triggering the stopping rule for mortality. If a mortality rate of 40% is observed, a 20% increase in mortality over the historical rate, there will be a 71.0% chance of triggering the stopping rule with 30 patients.

At every interim evaluation (t); a listing for patients who died including the cause of death will be produced along with any other data points deemed required.

**Table 5. Cumulative Stopping Probabilities for Mortality Rates at Day 56**

Evaluation (t)	Total N	X t	Cumulative Probabilities of Stopping at Evaluation (t) with Observed Mortality Rates	
			0.20	0.40
1	6	4	1.7%	17.9%
2	12	6	1.9%	33.5%
3	18	8	1.6%	43.7%
4	24	10	1.3%	51.0%
5	30	11	2.6%	71.0%

- A brief interim safety report summarizing AEs and SAEs will be generated when the first six patients have completed the day 86 visit. This will include all the AE and SAE summary tables and listings mentioned in this SAP. Note: This report will be generated after the 6th patient completes the day 86 visit. This report will include the first 6 patients only with all the safety data available at the time of data cut.
- Additionally, an informal interim analysis will occur after all patients have completed Day 56, which is the end of the treatment period. This interim analysis will

summarize the primary endpoint and other efficacy endpoints, up to day 56 assessment, with the exception of overall survival and non-relapse mortality. In terms of safety, treatment emergent AEs and SAEs will be summarized with all safety data available. The interim analyses will also summarize PK and PD results. Summary tables and listings will be produced for the following parameters as mentioned in this SAP: Enrollment Status, Patient Disposition (Treatment Period), Demographics, Primary Endpoint, Other Efficacy Endpoints (except overall survival and non-relapse mortality), Concomitant medications, treatment emergent AEs and SAEs.

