11.2. Adverse Event Management

The Investigator is responsible for detecting, assessing, documenting and reporting all AEs.

All AEs will be recorded from the signing of informed consent until 30 days after the last dose of ALXN1007. All SAEs will be recorded from signing of informed consent through the Day 180 visit. In addition, any notifications of death as a result of the Day 360 survival follow-up will also be recorded; the cause of death or event leading to death should be reported as an SAE.

(Note: There is no time limit for reporting SAEs that are considered causally related.)

All observed or volunteered AEs, regardless of causal relationship, must be reported and recorded in the eCRF. AEs reported by the subject, legal guardian, and/or identified in response to an open-ended question from study personnel, or revealed by observation, physical examination or other study procedures must be collected and recorded.

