### **4.1. Changes from Analyses Specified in the Protocol**

Following changes in analyses specified in the protocol are noted:

- Safety analyses will be only performed on safety set as opposed to both safety set and modified safety set as mentioned in the protocol.
- Demographics, baseline characteristics and medical history will be only summarized for safety set as opposed to safety set, modified full analysis set and per-protocol set as mentioned in the protocol.
- The imputation rule has been modified from that described in the protocol for overall acute GVHD response, acute GI-GVHD response and acute GVHD response involving all organs.

In addition due to early termination of the study, an abbreviated CSR will be written and a number of pre-specified analyses will not be performed however by-patient listings will be generated for all data collected for this study.

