#### **5.2.1. Adverse Events (AEs)**

Treatment-emergent adverse events (TEAE) will be defined as any adverse event with onset on or after 1st ALXN1007 administration.

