## **7. STATISTICAL ANALYSIS**

All statistical calculations will be performed using SAS, unless otherwise specified. All data will be presented in the form of listings sorted by treatment group (cohort) and patient ID. Tabular summaries will be presented based on the following grouping: 10mg/kg once weekly, 20mg/kg once weekly, 20mg/kg twice weekly and overall (all three treatment groups combined).

For continuous variables, summary statistics will include sample size, mean, standard deviation, median, minimum, and maximum values. Frequencies and percentages will be calculated for categorical variables. Graphical displays will be produced, as mentioned in this SAP.

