#### Adverse Events

If the start date of an AE is partially or completely missing and the end (stop) date and time of the AE does not indicate that it occurred prior to first dose, then the determination of treatment-emergent status will be based on the following:

- If the start year is after the year of the first study drug dose, then the AE is treatment-emergent; else,
- If the start year is the same as the year of the first study drug dose and
  - the start month is missing, then the AE is treatment emergent; else if
  - the start month is present and is the same or after the month of the first study drug dose, then the AE is treatment-emergent; else.
- If the start date is completely missing, then the AE is treatment-emergent.

All other AEs are considered Pre-Treatment Adverse Events (PTAEs).

Patient percentages are based on the total number of treated patients.

Related AEs are defined as possible, probable or definitely related. Unrelated AEs are defined as unlikely or not related.

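### The informal interim tabulates SAEs by dose cohort as crude percentages with no common cut-off, so SAEs in the later, higher-dose subjects are probably understated.

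*SAP*

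**What the plan says.** SAP section 7.4 states that "an informal interim analysis will occur after all patients have completed Day 56". At that cut it limits efficacy to the primary endpoint and "other efficacy endpoints, up to day 56 assessment, with the exception of overall survival and non-relapse mortality". The safety sentence that follows sets no such limit: "In terms of safety, treatment emergent AEs and SAEs will be summarized with all safety data available".

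Four other provisions determine what the safety tables will look like:

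- **Grouping.** SAP section 7: "Tabular summaries will be presented based on the following grouping: 10mg/kg once weekly, 20mg/kg once weekly, 20mg/kg twice weekly and overall".
- **Measure.** SAP sections 7.3.2.1 and 7.3.2.2 ask for numbers of events and number (%) of patients with events. SAP section 9.4 adds: "Patient percentages are based on the total number of treated patients".
- **Window.** The TEAE definition in SAP section 5.2.1 has a start (first dose) but no end, so the collection rules in protocol section 11.2 set the limit. Non-serious AEs stop 30 days after the last dose. For serious events, "All SAEs will be recorded from signing of informed consent through the Day 180 visit", and deaths learned of at the Day 360 contact are also reported as SAEs.
- **Order of entry.** Under protocol section 6.1, Cohort 1 (10 mg/kg weekly) comes first and Cohort 2 (20 mg/kg weekly) is added with Amendment 6. Cohort 3 (20 mg/kg twice weekly) is planned only after the DMC has reviewed Day 28 data on the first three Cohort 2 patients.

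No person-time rate, common safety window or summary of follow-up by cohort is specified. The heading of SAP section 7.3.1 mentions study duration and exposure, but its text tabulates only doses given.

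**The concern.** Safety across 10 to 40 mg/kg per week is part of the stated justification for the sample size (protocol section 13.2), and the by-cohort SAE tables are where doses will be compared. If follow-up shortens as dose rises, a crude percentage mixes dose with time at risk. With equal true risk, the cohort followed for less time shows fewer SAEs. The error runs in one direction and could mask a dose-related excess.

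Fatal events are exposed in the same way at this cut. The survival and non-relapse mortality analyses, which handle incomplete follow-up, are left out of the interim. Crude counts of TEAEs leading to death would then be the by-cohort view of mortality.

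**Working it through.** The plan states no follow-up figure by cohort and no expected SAE rate, so there is no figure of its own to reproduce. What follows is calendar arithmetic plus an illustration.

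**Inputs from the documents.** First subject November 2014 and last subject completed December 2017 (protocol synopsis); participation to Day 360; about 30 subjects (SAP section 4) or up to 36 (protocol section 6.2); Cohort 1 at most 18, Cohorts 2 and 3 three to about six each; last dose Day 49 (weekly) or Day 52 (twice weekly); Day 56 mortality of about 20% (protocol section 6.5.4).

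**Assumptions.** Even accrual, 30 subjects, and the last six are Cohort 3. November 2014 to December 2017 is 37 months; less 360 days leaves about 25 months of accrual.

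**Step 1: SAE follow-up at the interim.**
- Spacing = 25 × 30.4 / 29 = 26.2 days.
- Cohort 3: min(56 + 26.2i, 180) for i = 0 to 5 gives 56, 82, 108, 135, 161 and 180 days; mean 120.
- Last Cohort 1 subject, with 12 entering later: 56 + 12 × 26.2 = 370 days, so the 180-day window is complete. Last Cohort 2 subject: 56 + 6 × 26.2 = 213 days, also complete.

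**Step 2: share of Cohort 3's expected SAEs to Day 180 not yet observed.** Let the SAE rate after Day 56 be m times the earlier rate, with H(t) = min(t, 56) + m × max(t − 56, 0). The share is 1 − mean H(t) / H(180). For m = 1, this is 1 − 120.3/180 = 33%.

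| Case | m = 1 | m = 0.5 | m = 0.25 | m = 0.1 |
|---|---|---|---|---|
| 30 subjects, six in Cohort 3 | 33% | 25% | 17% | 9% |
| 36 subjects (spacing 21.7 days), six in Cohort 3 | 39% | 30% | 20% | 10% |
| 30 subjects, three in Cohort 3 (mean 82 days) | 54% | 41% | 28% | 14% |

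**Step 3: deaths.** With h = −ln(0.8)/56 and equal hazard in all cohorts, F(t) = 1 − exp(−h × H(t)).
- m = 1: 51% by Day 180 in Cohort 1, against a mean of 37% in six Cohort 3 subjects.
- m = 0.25: 29% against 25%.

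These count deaths to Day 180 only. Since later deaths are also reported as SAEs, the gap for fatal events could be wider.

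**Step 4: non-serious AEs.** Collection ends at Day 49 + 30 = 79 or Day 52 + 30 = 82. On the Step 1 times, five of the six Cohort 3 subjects have reached Day 82. The share of the window observed is (56 + 5 × 82) / (6 × 82) = 95%.

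**Step 5: how far Step 1 depends on accrual.** If cohorts do not overlap, the fastest permitted sequence gives the last Cohort 1 subject about 1 + 28 + 1 + 56 = 86 days at the interim (83 with visit windows). For that subject to have 180 days, the last Cohort 3 first dose must fall at least 180 − 56 = 124 days later. With 12 subjects after Cohort 1, this means accrual below 12/124 × 30.4 = 2.9 per month. The planned pace is about 30.4/26.2 = 1.2 per month.

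**The case against.** The strongest reply is that nothing turns on these tables. The interim is informal and descriptive and falls after all dosing. Escalation rests on DMC reviews at a common Day 28 (protocol sections 6.1 and 14.4), and the mortality rule uses a common Day 56 endpoint. In cohorts of six, the death differences above amount to 6 × (0.51 − 0.37) = 0.84 or 6 × (0.29 − 0.25), about a quarter, of one death, while the exact 95% interval for 2 of 6 runs from 4% to 78%. Protocol section 13.1 also asks for all TEAEs at this interim, so the SAP's wording follows it. All of this stands and limits the weight of the point. It does not remove a bias of known direction that is cheap to avoid.

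A reader might infer more than the documents support:

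- **That all TEAE tables are distorted.** The 30-day limit makes the effect on non-serious AEs small (Step 4).
- **That Cohort 1 certainly has 180 days and Cohort 3 has 56.** The first is inferred from planned dates; actual accrual is not given. The second is the last subject, not the cohort average. Further cohorts may also be added, so Cohort 3 need not be the last to enter.
- **That the final tables carry the same bias.** In a completed study every cohort has the same nominal Day 180 window, and survival is analysed by Kaplan-Meier with censoring. SAP section 4.1 says "In addition due to early termination of the study, an abbreviated CSR will be written", but it does not say that follow-up was cut short.

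**Conclusion.** The point holds for SAEs and fatal events at the informal interim. With no common safety window and crude percentages by cohort, the plan will probably understate events in the subjects who enter last, who on the planned sequence receive the highest dose. With 30 subjects, six in Cohort 3 and even accrual, about 9% to 33% of Cohort 3's expected SAEs to Day 180 are unobserved. The range reflects how sharply the SAE rate falls after Day 56. Three subjects in Cohort 3 would make the share larger; faster accrual after Cohort 1 could narrow the gap between cohorts.

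This is a gap in the plan, not a conflict between the documents, since the protocol sets no safety cut at this interim either. It does not show that dose escalation or the final safety tables are compromised. It is still worth correcting, because the by-cohort table invites a dose comparison that it cannot fairly support.

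**What to change.** In SAP section 7.4, keep the all-available-data TEAE and SAE tables, which the protocol calls for, and add:

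- (a) a by-cohort summary of TEAEs and SAEs with onset from first dose through Day 56, named as the table for comparing cohorts;
- (b) days of follow-up by cohort, with SAEs per subject-time to Day 180.

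Repeat (b) in SAP sections 7.3.1 and 7.3.2 for the final analysis, so that any truncation from early termination is visible.

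Table (a) should lead the comparison, because a subject-time rate is fair only if the rate is roughly constant. With m = 0.25, Cohort 3's rate would be (56 + 0.25 × 64.3)/120.3 = 0.60 of the early rate against 87/180 = 0.48 in Cohort 1, which tilts the other way.

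The cost is two or three extra tables from onset and last-contact dates already collected. Table (a) has one limit to footnote: Day 56 is only 4 days after the Day 52 dose in Cohort 3, against 7 days after the Day 49 dose in the weekly cohorts. Later events remain in the all-data tables and the by-patient listings.

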## **7.5. Data Monitoring Committee**

An independent Data Monitoring Committee (DMC) will conduct interim monitoring of safety data throughout the treatment period of the study. Refer to the study DMC Charter for all DMC procedures, processes and analysis for the study.

## 8 APPENDICES

### 9.1 Protocol Schedule of events

For the schedule of events/assessment, this SAP refers to the protocol version 8 dated 12 February 2016.

### 9.2 Changes from Analyses Specified in the Previous Version of the SAP

Not applicable

### 9.3 Sample Size, Power, and Randomization

Up to 36 patients confirmed by biopsy to have acute GI GVHD will be enrolled in this study. This sample size is felt to be sufficient for assessment of safety, tolerability, PK/PD, and efficacy of ALXN1007 at doses ranging from 10 mg/kg per week up to 40 mg/kg per week in patients with acute GI GVHD.

### 9.4 Technical Specifications for Derived Variables

The following derived data will be calculated prior to analysis.

#### Age

Age will be presented as the number of years between date of birth and the reference date. The following age will be computed, with reference dates indicated:

**Table 6. Age and reference date**

AGE	REFERENCE DATE
• Age at Enrollment	• Date of Signing ICF

For all dates, in cases where only the month and year are provided for a date, the day for the date will be imputed as 15. Missing month will be imputed as June. In cases where the day is observed but the month is missing, the date will be imputed as June 15.

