## 5. DEFINITIONS

### 5.1. Efficacy

#### Secondary Therapy

A key factor in several of the efficacy parameters is determination of secondary therapy (re-escalation of steroid and/or additional intervening therapy) which may consist of any of the following changes to background therapy during the study treatment period:

1. Re-escalation: 2.5mg/kg/day prednisone equivalent for 2 consecutive days starting on or after Day 6 (note, the day of 1st ALXN1007 is denoted by Day 1 for analysis purpose)
2. Additional systemic therapy for treatment of GVHD (including but not limited Biologics/anti-TNF or Antineoplastic medications administered post-baseline for treatment of GVHD)

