#### **5.1.2.8. Overall Survival**

Assessment of overall survival at Days 180 and 360 will be measured based on the time (days) since 1st ALXN1007 dose to death due to any reason. Patients with incomplete follow-up for other reasons will be censored.

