### **7.1.4. Prior and Concomitant Medications / Therapies**

Prior medications are defined as medications taken or therapies received by patients prior to the first dose of ALXN1007. Concomitant medications are defined as medications taken or therapies received by patients during the study after first dose of ALXN1007. Medications will be coded using the World Health Organization Drug Dictionary version. Summaries will be performed on the Safety set. A medication will be considered conservatively both prior and concomitant if partial start or stop dates are recorded such that its designation as a prior and/or concomitant medication could not be determined with certainty.

The number (%) of patients taking prior and concomitant medications will be summarized based on the World Health Organization Anatomical Therapeutic Chemical (WHO ATC) Level 1 and generic name. In addition, by-patient listings will be provided for the following:

- Prior investigational agents
- Secondary therapies (during the study)

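### The SAP's 15th/June rule for partial dates covers all dates with no bound at first dose or last date known alive, so a partial date can misplace rescue therapy or death

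*SAP*

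**What the plan says.** The rule stands in SAP 9.4, directly below Table 6 on age. It reads "For all dates, in cases where only the month and year are provided for a date, the day for the date will be imputed" as the 15th. It continues "Missing month will be imputed as June", and then "In cases where the day is observed but the month is missing, the date will be imputed as June 15". The last clause throws away a day that was recorded. No clause ties the imputed date to the first dose, to an assessment or to the last date known alive.

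Three sets of rules use dates on a scale of days from first dose:

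- **Secondary therapy (SAP 5.1).** Steroid re-escalation counts if it is "2.5mg/kg/day prednisone equivalent for 2 consecutive days starting on or after Day 6", with the first dose as Day 1. Other systemic therapy counts if it is post-baseline, for example "Antineoplastic medications administered post-baseline for treatment of GVHD". Under SAP 5.1.2.1 and 5.1.2.2, secondary therapy makes a patient a non-responder unless progression applies first.
- **Missing responses (SAP 7.2.1.1 and 7.2.2.1).** Whether a missing visit is scored as non-response or takes the last response forward depends on whether secondary therapy or death came before it. The worked example in 7.2.2.1 turns on Day 28.
- **Survival (SAP 5.1.2.8).** "Assessment of overall survival at Days 180 and 360 will be measured based on the time (days) since" the first dose to death.

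Two other rules deal with partial dates. SAP 7.1.4 says "A medication will be considered conservatively both prior and concomitant if partial start or stop dates are recorded" in a way that leaves the label uncertain. The adverse-event paragraph of SAP 9.4 decides treatment-emergent status.

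**The concern.** A mid-month or mid-year default does little harm to age in years. It is coarse for a primary endpoint at Day 28 with a threshold at Day 6. Filling in the 15th shifts a date by -16 days (true day the 31st) to +14 days (true day the 1st). Filling in 15 June shifts it by -199 days (from 31 December) to +166 days (from 1 January of a leap year). These shifts are large against a 28-day window.

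If a rescue date leaves the qualifying window, a patient whose staging improved can be scored as a responder despite rescue. If a later rescue is pulled back across Day 28, a true Day 28 responder can be scored as a non-responder. A death placed before first dose gives a zero or negative survival time, for which the SAP has no rule.

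**Working it through.** The plan gives no figure for this rule, so there is none to reproduce. The check applies the rule to calendar dates.

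**Inputs from the documents.** First dose is Day 1 and re-escalation counts from Day 6 (SAP 5.1). The imputed date is the 15th, or 15 June (SAP 9.4). Cohort sizes are 18 at most, or 3 to about 6 (protocol 6.2). Intervals are Clopper-Pearson (SAP 7.2.1).

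**Assumptions not in the documents.** First doses are spread evenly over 1 November 2014 to 30 November 2016 (761 dates). True event days are uniform within each window.

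**Formula.** Imputed day = (imputed date - first-dose date) + 1. A re-escalation truly on Days 6-28 is lost for Day 28 if its imputed day is below 6 or above 28.

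**Single cases**

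| First dose | True event | Missing | Imputed | Result |
|---|---|---|---|---|
| 20 Mar 2016 | 28 Mar, Day 9 | day | 15 Mar | 5 days before first dose |
| 13 Feb 2016 | 3 Mar, Day 20 | day | 15 Mar, Day 32 | moved past Day 28 |
| 20 Feb 2016 | 25 Mar, Day 35 | day | 15 Mar, Day 25 | pulled before Day 28 |
| 5 Sep 2016 | 20 Sep, Day 16 | month | 15 Jun | 82 days before first dose |

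**All dates, day missing**

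- Re-escalation truly on Days 6-28 (761 x 23 = 17,503 combinations): 8.6% land before first dose, 9.6% on Days 1-5 and 15.0% after Day 28. Lost: 8.6 + 9.6 + 15.0 = 33.2%.
- If the Day 28 visit is analysis Day 29, because baseline is Day 1, the sum is 8.2 + 9.2 + 14.4 = 31.8%.
- Any event truly on Days 1-28 (relevant to additional systemic therapy, which has no Day 6 test): 14.9% land before first dose and 12.3% after Day 28.
- Events truly on Days 29-56: 15.0% land on or before Day 28.
- Deaths truly on Days 1-56: 7.5% land before first dose.
- Survival landmark: 11.1% of deaths truly on Days 150-180 move past Day 180, and 14.0% of those on Days 181-210 move to Day 180 or earlier.

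**All dates, month missing.** Of events truly on Days 1-28, 52.7% land before first dose and 39.9% after Day 28.

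**One patient reclassified (illustrative counts).** With n = 18, going from 9 to 10 responders moves 50.0% (95% CI 26.0-74.0) to 55.6% (30.8-78.5), and 1/18 = 5.6 points. With n = 6, going from 3 to 4 moves 50.0% (11.8-88.2) to 66.7% (22.3-95.7).

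**A simple remedy that fails.** Suppose therapy start is set to the earliest compatible date, floored only at first dose. With first dose on 5 March and re-escalation on 14 March (Day 10), the current rule gives 15 March, Day 11, which counts. The simple remedy gives 5 March, Day 1, which fails the Day 6 test. Over the same 17,503 combinations it loses 61%, against 33% now. With the floor at Day 6 for re-escalation the loss is 0%, because the imputed day can be neither below 6 nor later than the true day.

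**The case against.** The case for leaving the text alone has several parts.

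- **Scope.** The sentence sits under the age heading, so it may have been meant for birth dates. That is plausible, but the wording covers all dates and a programmer would have to follow it.
- **Other rules.** SAP 7.1.4 keeps an ambiguous drug in the concomitant group, so a reader who infers a flat contradiction with SAP 9.4 goes too far. One rule is specific and the other general, and they are not reconciled. SAP 7.1.4 still does not say whether the drug meets the Day 6 test or precedes Day 28, and it does not cover death.
- **Frequency.** Protocol 10.2.5 and 10.2.6 record immunosuppressant and corticosteroid use at every visit. Protocol 11.2.5 makes the date of death the end date of the fatal event. Partial dates should be few, and a missing month rarer still. Deaths learned of at the Day 360 telephone contact are the likeliest source. This stands, and it limits the size of the problem.
- **Absorption.** For GI and all-organ response, SAP 7.2.2.1 scores a death inside a visit's analysis window as progression, which may absorb small shifts. The window widths are not given, and the primary rule in SAP 7.2.1.1 has no such clause. A death that stays on the same side of Day 180 or 360 barely changes the Kaplan-Meier estimate there.
- **Stakes.** There is no formal testing, the report is abbreviated, and secondary therapies are listed by patient. The listing may expose a bad date but prescribes no correction.

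A reader might also infer that the rule always flatters the drug. The documents do not support that. Losing rescue can only raise the response rate or leave it unchanged, because a patient without improvement is a non-responder anyway. Pulling later rescue back across Day 28 can lower the rate.

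**Conclusion.** The point holds as a defect in the imputation rule. Followed as written, SAP 9.4 can place secondary therapy or death before first dose, before Day 6 or on the wrong side of Day 28. No other rule in the SAP settles that timing.

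With the day missing, about one re-escalation in three truly on Days 6-28 is lost, and about 15% of events on Days 29-56 are pulled to Day 28 or earlier. These figures are conditional on a partial date and rest on the assumed uniform timing. They do not estimate the error in the reported response rate, and the large month-missing percentages should not be read that way. The documents do not say how many dates are partial. The direction of any net bias is not known. The correction is worth making because cohorts are small and it costs little.

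**What to change.** Amend SAP 9.4 as follows.

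- Limit the 15th/June rule to date of birth and medical history.
- For secondary therapy recorded as starting after first dose, impute the earliest date compatible with the recorded parts, including a known day, and with the definition in SAP 5.1. That means not before first dose for additional systemic therapy and not before Day 6 for steroid re-escalation. Use the visit-level medication records to narrow the range first.
- For death, never impute earlier than the day after the patient was last known alive.
- State how this rule relates to SAP 7.1.4.
- Report a sensitivity analysis using the latest compatible date, with the number of imputed dates.

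The cost is a few lines of text and derivation code. The downside is that some therapy truly started after Day 28 will be counted as earlier. With first dose on 20 February 2016 and re-escalation on 25 March (Day 35), the earliest date is 1 March, Day 11. In the same enumeration, before visit records narrow the range, about 52% of re-escalations truly on Days 29-56 with the day missing would be pulled to Day 28 or earlier. The main result therefore leans against the drug, though only slightly if partial dates are few, and the latest-date analysis shows how much depends on that choice. Nothing changes where dates are complete.
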